5.3 STRATEGIES FOR RECRUITMENT AND RETENTION

Up to 50 subjects will be enrolled at up to 5 sites. It is anticipated that it will take up to twelve months to complete the study. Subjects requesting non-invasive lipolysis of the abdomen will be recruited primarily from the investigator's clinic. Any advertising campaigns and materials will be reviewed and approved by an institutional review board (IRB) before implementation. Due to the duration of the study, subjects will be contacted by the investigative site on a regular basis in order to enhance retention.

5.4 PARTICIPANT WITHDRAWAL OR TERMINATION

5.4.1 REASONS FOR WITHDRAWAL OR TERMINATION

Subjects are free to withdraw from participation in the study without prejudice at any time upon request. In the event that a subject drops out of the study or is withdrawn from the study, the End of Study/Early Discontinuation CRF form should be completed. On the withdrawal page, the Investigator should record the date of the withdrawal and the reason for withdrawal.

Reasonable effort should be made to contact any subject lost to follow up during the course of the study in order to complete assessments and retrieve any outstanding data. The records of subjects who terminate prior to completing the study will be retained and the reason for termination will be documented.

An investigator may terminate participation in the study if:

- Any clinical adverse event (AE), laboratory abnormality, or other medical condition or situation occurs such that continued participation in the study would not be in the best interest of the subject.
- The subject meets an exclusion criterion (either newly developed or not previously recognized) that precludes further study participation.

5.4.2 HANDLING OF PARTICIPANT WITHDRAWALS OR TERMINATION

Every effort will be made to continue follow-up of withdrawn or terminated subjects or subjects who discontinue the intervention but remain in the study for follow-up, especially for safety and efficacy study endpoints. Every effort will be made to conduct a final visit and undertake protocol-specified safety follow-up procedures to capture AEs, serious adverse events (SAEs), and unanticipated problems (UPs).

5.5 PREMATURE TERMINATION OR SUSPENSION OF STUDY

The sponsor may suspend or prematurely terminate this study at an individual investigation site or the entire study for significant and documented reasons.

A principal investigator (PI), IRB, or regulatory authority may suspend or prematurely terminate participation in the study at the investigation site for which they are responsible.

If suspicion of an unacceptable risk to subjects arises during the study, or when so instructed by the IRB or regulatory authorities, the sponsor shall suspend the clinical investigation while the risk is assessed. The sponsor shall terminate the study if an unacceptable risk is confirmed.

The sponsor shall consider terminating or suspending the participation of the investigation site or investigator in the study if monitoring or auditing identifies serious or repeated deviations on the part of an investigator.

If suspension or premature termination occurs, the terminating party shall justify its decision in writing and promptly inform the other parties with whom they are in direct communication. The principal investigator and sponsor shall keep each other informed of any communication received from either the EC/IRB or the regulatory authority.

If, for any reason, the sponsor suspends or prematurely terminates the study at the investigation site, the sponsor shall inform the responsible regulatory authority as appropriate and ensure that the EC/IRB is notified, either by the principal investigator or by the sponsor. If the suspension or premature termination was in the interest of safety, the sponsor shall inform all other principal investigators.

If suspension or premature termination occurs,

- a) the sponsor shall remain responsible for providing resources to fulfil the obligations from the protocol and existing agreements for following up the subjects enrolled in the study, and
- b) the principal investigator or authorized designee shall promptly inform the enrolled subjects at the investigation site, if appropriate

In case of early termination, final study activities according to the protocol, including the follow-up visits and procedures to assess the safety and efficacy of the device will be conducted, regardless of the sponsor's interest in the study. Follow-up activities will be conducted so that device deficiencies can be identified, and appropriate safety measures can be implemented.

At the completion or termination of the study, the Investigator will return all remaining clinical supplies to Sponsor along with a copy of the device supply and inventory records.

Circumstances that may warrant termination or suspension include, but are not limited to:

- Determination of unexpected, significant, or unacceptable risk to participants (examples of findings that might trigger a safety review are the number of SAEs overall, the number of occurrences of a particular type of SAE, severe AEs/reactions, or increased frequency of events – refer to section 8.5 STUDY HALTING RULES).
- Demonstration of performance that would warrant stopping
- Insufficient compliance to protocol requirements
- Data that are not sufficiently complete and/or evaluable
- Determination of futility

Study may resume once concerns about safety, protocol compliance, data quality and the like as the case may be are addressed and satisfy the sponsor, IRB and/or regulatory authorities.

6 STUDY DEVICE

6.1 STUDY DEVICE AND CONTROL DESCRIPTION

6.1.1 ACQUISITION

The Venus Bliss™ investigational device will be shipped to the investigative site directly from the sponsor. Training on the use of the device will be provided by the sponsor. The investigative site will not perform any treatments until all regulatory and IRB approvals are in place and the site has received training for both devices and the study.

6.1.2 DEVICE SPECIFIC CONSIDERATIONS

The Venus BLISS™ investigational device is a 1060nm diode laser system intended for non-invasive lipolysis of the abdomen in individuals with a Body Mass Index (BMI) of less than 30. The device consists of a console, four laser applicators and a belt that secures the laser applicators in place securely to the subject's selected treatment area. Each applicator includes contact tissue cooling and has an active area of 60mm x 60mm.

The clinician is able to control the settings from the graphical user interface (GUI) display on the main console. The available settings for this applicator is:

- Optical power up to 1.4 W/cm² at 1060nm

Treatment time is 25 minutes.

6.2 STUDY DEVICE ACCOUNTABILITY PROCEDURES

The device and applicators will be shipped to the site by the sponsor. Traceability shall be achieved during and after the clinical investigation by assignment of serial numbers to device and applicators and accounting for the device and applicators returned to the sponsor by each site.

The device will be labeled as an investigational device and will require protocol and device training from the sponsor.

7 STUDY PROCEDURES AND SCHEDULE

7.1 STUDY PROCEDURES/EVALUATIONS

7.1.1 STUDY SPECIFIC PROCEDURES

The following procedures and evaluations will be done as part of the study:

Demographics

Medical / surgical history

Physical examination (as per site's standard of care)

Assessment of eligibility

Urine pregnancy test for women of child bearing potential (visit 1 only)

Treatment area marking

Abdominal circumference measurements

Photographs (visit 1, visit 2 and visit 3)

Ultrasound subcutaneous fat (visit 1, visit 2 and visit3)

Administration of a questionnaires/scales for patient-reported outcomes (visit 1 and visit 3 only)

Adverse event recording

Concomitant medications

7.2 LABORATORY PROCEDURES/EVALUATIONS

7.2.1 CLINICAL LABORATORY EVALUATIONS

For women of child-bearing potential, urine pregnancy test to be performed according to local site standards within 24 hours of study intervention. Results must be available prior to administration of the treatment.

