5 STUDY ENROLLMENT AND WITHDRAWAL

5.1 PARTICIPANT INCLUSION CRITERIA

1. Able to read, understand and voluntarily provide written informed consent .
2. Healthy male or female, ≥ 18 years of age seeking treatment for unwanted fat in the abdomen.
3. BMI score is less than 30.
4. Agree to not making any major changes in their diet or lifestyle during the course of the study.
5. Able and willing to comply with the treatment/follow-up schedule and requirements.
6. Women of child-bearing age are required to be using a reliable method of birth control at least 3 months prior to study enrollment and for the duration of the study, and have a negative Urine Pregnancy test at baseline.

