7.3 STUDY SCHEDULE

7.3.1 SCREENING

Screening Visit

If the subject meets the preliminary study criteria the study doctor, and/or his/her designee, will obtain an informed consent from the subject, clearly indicating his/her understanding of the requirements and possible risks involved with study participation and other applicable treatment options. Subjects will receive a unique identifying number that will be composed of a two-digit site number and a three digit subject number in sequence. This unique identifier will be used throughout the entire study and will be entered in the subject's case report form (CRF) and for each treatment.

During screening visit, the study investigator, and/or his/her designee, will assess the subject for eligibility to participate in the clinical study using the inclusion/exclusion criteria. A urine sample for the pregnancy test will be obtained for female subjects of child-bearing potential. During screening, the study doctor will review the subject's medical/surgical history and examine the target treatment areas to ensure they meet the study criteria.

Subjects will be instructed to avoid sun exposure of the target treatment areas for at least six weeks before treatment and to use broad spectrum sunscreen of no less than 30 SPF daily, replenishing it as often as needed throughout the course of the study and for six weeks after the treatment. In addition, tanning is to be strictly avoided. Subjects should not receive any treatment with a laser or other devices in the study treatment area throughout the course of this study and follow-up examinations.

The investigator will ask women of child-bearing potential for the date of their last period. The investigator shall inquire about the form of contraceptive they use to confirm they meet the inclusion criteria.

The subject will complete screening and the treatment will be scheduled. Treatment may be performed on the day the subject was enrolled if the results of the urine pregnancy test are available (and negative) and the subject has avoided sun exposure of the target treatment area for at least six weeks.

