7.3.2 ENROLLMENT/BASELINE

Enrollment/Baseline/Treatment Visit (Visit 1 – Day 0)

Pre-Treatment

The investigator will confirm that the subject continues to meet the inclusion and none of the exclusion criteria. Adverse events, weight and any changes to concomitant medications will be recorded. The subject will complete the modified Simple Lifestyle Indicator Questionnaire (SLIQ).

The location and size of the treatment area will be left to the principal investigator's judgement based on his/her assessment of individual subject requirements for treatment. The defined abdominal treatment area will be marked with a semi-permanent pigment using a treatment template as per the sponsor's instructions. Photographs of the marked treatment area followed by ultrasound measurements of the marked treatment area will be made as per the instructions supplied by the sponsor. Measurement of the abdominal circumference will be made with the sponsor supplied tape measure using the marked boundaries as a guide for replication.

Treatment

Protective eye goggles will be worn by both the patient and site staff performing the treatment for the duration of the treatment session.

Based on the mild nature of treatment, anesthesia is not required. The treatment procedure should include positioning of the patient in a manner that enables access to the target treatment anatomical site.

The belt will be positioned on the subject as per the marked treatment template. Laser applicators will be secured in place by the belt with the areas treated for up to 25 minutes. The laser energy will be delivered to the area while cooling is administered to the skin surface to increase subject comfort. Treatment will continue until the total treatment area has been treated. The subject will receive one treatment session only.

The assessment of discomfort/pain during the treatment procedure will be assessed using the Wong-Baker Faces Pain rating scale with treatment parameters adjusted according to patient's comfort level.

Post Treatment

Assessment

The investigator will examine the treated areas and report immediate response (pain during treatment, hemorrhage, burn, erythema, edema, purpura) using a 5 point scale: 1=none; 2=trace; 3=moderate; 4=marked; 5=severe.

The assessment of discomfort/pain based on the subject's completion of the 10 cm visual pain scale should also be documented immediately after treatment.

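### The 24-hour pregnancy-test rule in 7.2.1 is not carried into the visit instructions, which place the test at screening and name none at Visit 1

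*Combined protocol and SAP*

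**What the plan says.** Three provisions tie the urine pregnancy test to treatment:

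- Section 7.2.1 asks for a "urine pregnancy test to be performed according to local site standards within 24 hours of study intervention" and adds: "Results must be available prior to administration of the treatment".
- Section 7.1.1 lists the procedure as "Urine pregnancy test for women of child bearing potential (visit 1 only").
- Inclusion criterion 6 in section 5.1 requires women of child-bearing age to "have a negative Urine Pregnancy test at baseline". Section 7.3.2 heads Visit 1, Day 0 as the enrollment, baseline and treatment visit, so baseline here is the day of treatment.

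The visit-by-visit text places it elsewhere:

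- Section 7.3.1, describing the screening visit, says: "A urine sample for the pregnancy test will be obtained for female subjects of child-bearing potential".
- The pre-treatment steps in section 7.3.2 cover eligibility, adverse events, weight, medications, the lifestyle questionnaire, marking, photographs, ultrasound and circumference. No pregnancy test is among them.
- The Schedule of Events Table has one mark for the test, in the screening column, which is headed minus six weeks. There is none under Visit 1.

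**The concern.** A site runs each visit from the visit narrative and the schedule. Followed literally, these lead it to test at screening and not again. Where screening and treatment are more than 24 hours apart, the subject could then be treated on a result that 7.2.1 regards as too old.

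What is at stake is a possible early pregnancy missed at treatment, and avoidable deviations from 7.2.1. The study may use up to five sites, and they could resolve the conflict differently. This is a safety and conduct point. It does not touch any endpoint, the error rate or the power.

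**Working it through.** The plan gives no figure to reproduce. The check sets the provisions side by side and then works out how old a screening test could be at treatment.

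**Step 1: where each provision puts the test**

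| Place | Timing of the test |
|---|---|
| 7.2.1 | Within 24 hours of treatment, result known first |
| 7.1.1 | Visit 1 and no other visit |
| 5.1, criterion 6 | Negative at baseline (Visit 1, Day 0) |
| 7.3.1 | Screening visit |
| 7.3.2, pre-treatment steps | No test named |
| Schedule of Events Table | Screening column only |

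The first three rows can be reconciled with the last three only if treatment follows the screening test within 24 hours.

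**Step 2: are separate visits foreseen?**

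They are. Section 7.3.1 says that treatment is scheduled once screening is complete. It makes same-day treatment optional: "Treatment may be performed on the day the subject was enrolled if the results of the urine pregnancy test are available (and negative"), and only if six weeks of sun avoidance are already complete. The same section gives the instruction at screening: "Subjects will be instructed to avoid sun exposure of the target treatment areas for at least six weeks before treatment". A subject who has not already avoided the sun has to wait.

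**Step 3: age of a screening test at treatment**

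- Sun-avoidance requirement (7.3.1): 6 weeks × 7 = 42 days.
- Let d be the days of avoidance already completed at screening.
- Shortest wait from screening to treatment = max(0, 42 − d) days.
- Limit in 7.2.1: 24 hours = 1 day.

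| d (days completed at screening) | Shortest wait = age of screening test | Within the 1-day limit? |
|---|---|---|
| 42 | 0 days | Yes |
| 41 | 1 day | Just |
| 28 | 14 days | No |
| 14 | 28 days | No |
| 0 | 42 days | No |

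A screening test alone can therefore satisfy 7.2.1 only if d is at least 41 and treatment follows within a day. The table assumes treatment as soon as the rule allows; later scheduling makes the test older. The plan does not say whether the minus six weeks in the schedule is a maximum window. If it is, 42 days is also the ceiling.

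**The case against.** The strongest reply is that the requirement exists and nothing relaxes it. Section 7.2.1 is unconditional, and no text says that a screening result is enough. Testing at screening and again within 24 hours of treatment would satisfy every provision except the restriction to Visit 1 in 7.1.1. Visit 1 also has its own check: "The investigator will confirm that the subject continues to meet the inclusion and none of the exclusion criteria". Read with criterion 6, that implies a negative test at baseline. On this view the protocol has a drafting gap, and a site that treats on an old result has overlooked an explicit rule.

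Much of this stands: the rule is present, and the problem is conflicting instructions. But the plan states no order of precedence, and the Visit 1 check does not ask for a new test. The only result scheduled for the investigator to check against is the one from screening. The schedule repeats the eligibility mark at Visit 1 but not the pregnancy-test mark.

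Two further points are fair:

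- **The schedule row.** It carries a footnote marker whose text is not available, and that footnote could qualify the row. The conflict of 7.3.1 and 7.3.2 with 7.1.1 and 7.2.1 stands without the table.
- **Other protections.** Reliable contraception is required from at least three months before enrollment, women intending pregnancy are excluded, and last period and contraceptive method are asked about at screening. The device is also classed as non-significant risk. These lower the chance of harm, but the protocol asks for a test in addition to contraception.

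**Conclusion.** The inconsistency is real and should be corrected. It matters only for women of child-bearing potential whose screening and treatment are more than 24 hours apart. For them, the visit instructions allow a test up to 42 days old where 7.2.1 allows 1 day. That range assumes treatment at the earliest date the sun-avoidance rule permits and a site that relies on the screening test alone. The documents do not say how many subjects would have such a gap, so the number affected cannot be estimated.

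**What to change.** Apply the 7.2.1 rule throughout:

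1. In the Schedule of Events Table, add a mark for the test at Visit 1, specified as before treatment, within 24 hours of it, and with a negative result required to proceed.
2. Add the same step to the pre-treatment list in 7.3.2.
3. In 7.3.1 and the schedule, either delete the screening test or state that it is additional and does not replace the Visit 1 test unless treatment follows within 24 hours.
4. If the screening test is kept, remove the restriction to Visit 1 in 7.1.1.

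The cost is one table mark, a few lines of text, and at most one extra urine test for each woman of child-bearing potential who is not treated within 24 hours of screening.

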7.3 STUDY SCHEDULE

7.3.1 SCREENING

Screening Visit

If the subject meets the preliminary study criteria the study doctor, and/or his/her designee, will obtain an informed consent from the subject, clearly indicating his/her understanding of the requirements and possible risks involved with study participation and other applicable treatment options. Subjects will receive a unique identifying number that will be composed of a two-digit site number and a three digit subject number in sequence. This unique identifier will be used throughout the entire study and will be entered in the subject's case report form (CRF) and for each treatment.

During screening visit, the study investigator, and/or his/her designee, will assess the subject for eligibility to participate in the clinical study using the inclusion/exclusion criteria. A urine sample for the pregnancy test will be obtained for female subjects of child-bearing potential. During screening, the study doctor will review the subject's medical/surgical history and examine the target treatment areas to ensure they meet the study criteria.

Subjects will be instructed to avoid sun exposure of the target treatment areas for at least six weeks before treatment and to use broad spectrum sunscreen of no less than 30 SPF daily, replenishing it as often as needed throughout the course of the study and for six weeks after the treatment. In addition, tanning is to be strictly avoided. Subjects should not receive any treatment with a laser or other devices in the study treatment area throughout the course of this study and follow-up examinations.

The investigator will ask women of child-bearing potential for the date of their last period. The investigator shall inquire about the form of contraceptive they use to confirm they meet the inclusion criteria.

The subject will complete screening and the treatment will be scheduled. Treatment may be performed on the day the subject was enrolled if the results of the urine pregnancy test are available (and negative) and the subject has avoided sun exposure of the target treatment area for at least six weeks.

7.3.2 ENROLLMENT/BASELINE

Enrollment/Baseline/Treatment Visit (Visit 1 – Day 0)

Pre-Treatment

The investigator will confirm that the subject continues to meet the inclusion and none of the exclusion criteria. Adverse events, weight and any changes to concomitant medications will be recorded. The subject will complete the modified Simple Lifestyle Indicator Questionnaire (SLIQ).

The location and size of the treatment area will be left to the principal investigator's judgement based on his/her assessment of individual subject requirements for treatment. The defined abdominal treatment area will be marked with a semi-permanent pigment using a treatment template as per the sponsor's instructions. Photographs of the marked treatment area followed by ultrasound measurements of the marked treatment area will be made as per the instructions supplied by the sponsor. Measurement of the abdominal circumference will be made with the sponsor supplied tape measure using the marked boundaries as a guide for replication.

Treatment

Protective eye goggles will be worn by both the patient and site staff performing the treatment for the duration of the treatment session.

Based on the mild nature of treatment, anesthesia is not required. The treatment procedure should include positioning of the patient in a manner that enables access to the target treatment anatomical site.

The belt will be positioned on the subject as per the marked treatment template. Laser applicators will be secured in place by the belt with the areas treated for up to 25 minutes. The laser energy will be delivered to the area while cooling is administered to the skin surface to increase subject comfort. Treatment will continue until the total treatment area has been treated. The subject will receive one treatment session only.

The assessment of discomfort/pain during the treatment procedure will be assessed using the Wong-Baker Faces Pain rating scale with treatment parameters adjusted according to patient's comfort level.

Post Treatment

Assessment

The investigator will examine the treated areas and report immediate response (pain during treatment, hemorrhage, burn, erythema, edema, purpura) using a 5 point scale: 1=none; 2=trace; 3=moderate; 4=marked; 5=severe.

The assessment of discomfort/pain based on the subject's completion of the 10 cm visual pain scale should also be documented immediately after treatment.

The normal response to this treatment is transient tenderness, edema and/or induration in the treated area which should resolve within one to two weeks. If any other side effects occur or persist for longer than expected, they must be recorded in the adverse event (AE) section of the case report form (CRF).

For post-treatment cooling and/or discomfort, cold packs can be applied to treatment area if needed with acetaminophen at recommended doses used to alleviate pain as needed.

During the day following treatment, care should be taken to prevent any mechanical or thermal damage to the treated sites: avoid hot baths, massage, contact sports, swimming, etc. The treated areas should be kept clean to avoid contamination or infection. The subject should be reminded to not make any major changes in their diet or lifestyle during the course of the study.

Subjects will be discharged from the clinic and will be scheduled to return for the six week assessment.

7.3.3 FOLLOW-UP 1

Visit 2, Week 6 (\pm 3 days)

Subjects will return to the clinic six weeks after the treatment. Adverse events, weight and any changes to concomitant medications will be recorded.

Measurement of the abdominal circumference will be made with the sponsor supplied tape measure using the marked boundaries as a guide for replication.

Photographs of the marked treatment area followed by ultrasound measurements of the marked treatment area will be made as per the instructions supplied by the sponsor.

Subjects will be discharged from the clinic and will be scheduled to return for the Twelve week (Final) assessment.

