2.3 POTENTIAL RISKS AND BENEFITS

2.3.1 KNOWN POTENTIAL RISKS

Expected adverse events of the laser treatment procedure include transient tenderness, erythema, edema, and/or induration in the treated area lasting from one to three weeks after the treatment. In addition, other adverse events may include and include localized firmness, ecchymosis, skin burn, hyperpigmentation, hypopigmentation, blister and changes in skin laxity. Rarely, skin contour irregularities, dimpling, asymmetry (uneven appearance due to uneven anatomy or uneven treatment of the area), necrosis (tissue death), hardness and nodules occur. Protective laser eyewear will be worn by the subject and operator providing the procedure.

The device has a contact tissue cooling system in place during the procedure to minimize thermal discomfort and prevent damage to the treatment area. Expected adverse events related to the contact cooling include tingling, itching, decreased sensation, numbness, erythema and tenderness.

The boundaries of the treatment area will be marked with a semi-permanent tattoo ink using a microblade. The ink markings should dissipate within one year. Microblade marking may be associated with tenderness.

There are minimal risks associated with the use of ultrasound. The use of the ultrasound may cause redness of the skin. Skin rashes rarely occur with the use of ultrasound gel.

Risks will be mitigated by conducting this protocol with an investigator experienced in the therapeutic area of the clinical investigation. The investigator will be trained by the sponsor on the use of the device. The device design incorporates safety mechanisms which minimize risks. Patients will also be rigorously screened prior to their enrollment and rigorously followed over the course of the study.

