4.2.1 PRIMARY ENDPOINTS

- Photographic evaluation by independent, blinded reviewers with correct identification of pre-treatment baseline images when compared to post-treatment images taken at twelve weeks

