4.2.2 SECONDARY ENDPOINTS

- To determine the change in thickness of the adipose layer as measured by ultrasound at twelve weeks post-treatment as compared to baseline
- To determine the change in abdominal circumference at twelve weeks post-treatment as compared to baseline
- To assess subject satisfaction with treatment at twelve weeks using the 5-Point Likert Subject Satisfaction Scale

Safety Endpoints:

- Report subject's assessment of discomfort and pain as measured by the Wong-Baker Faces Pain rating scale.
- Report subjects experiencing a treatment-related adverse event (AE).

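### Baseline and week-12 photographs both show the semi-permanent skin marks, and nothing in the protocol hides those marks from the blinded reviewers, so ageing ink may reveal which image came first

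*Combined protocol and SAP*

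**What the plan says.** **Marking.** Section 2.3.1 says the boundaries of the treatment area "will be marked with a semi-permanent tattoo ink using a microblade", and adds: "The ink markings should dissipate within one year". Section 7.3.2 places this step at Visit 1 before treatment: the area "will be marked with a semi-permanent pigment using a treatment template".

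**Photographs.** After marking, still before treatment, section 7.3.2 states: "Photographs of the marked treatment area followed by ultrasound measurements of the marked treatment area will be made". Section 10.4.1 defines baseline as the last photograph before treatment at Visit 1, so the baseline image shows the marks. Sections 7.3.3 (week 6) and 7.3.4 (week 12 ± 7 days) again call for photographs of the marked area. At all three visits the photographs follow sponsor instructions that are not reproduced in the protocol.

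**Endpoint.** Section 4.2.1 defines the primary endpoint as photographic evaluation by blinded reviewers with "correct identification of pre-treatment baseline images when compared to post-treatment images taken at twelve weeks". Section 10.4.2 sets success at an average of 80% correct. Section 10.2 applies no statistical hypothesis to this endpoint.

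**Blinding.** Section 10.6.1 covers subject numbering and states that subjects are not randomized. Section 10.6.2 says that only the independent reviewers are blinded. Section 10.6.3 is marked not applicable. Neither these sections nor 10.4.2 describe how images are prepared for review.

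**The concern.** The reviewers' task is to say which image came first. Anything in the images that changes with time, and not only the fat layer, can help them answer. Semi-permanent ink that the protocol expects to disappear is an obvious candidate.

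In a controlled design such a cue would affect both arms and much of it would cancel. Here there is no control arm, no null rate and no test. A pair identified from the ink and a pair identified from visible fat reduction score the same and enter the same 80% average.

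The secondary endpoints, ultrasound fat thickness ("To determine the change in thickness of the adipose layer as measured by ultrasound at twelve weeks post-treatment as compared to baseline") and abdominal circumference, do give separate evidence on fat, and ultrasound sets the sample size in section 10.5. They do not enter the primary decision in section 10.4.2, so they cannot correct it.

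**Working it through.** **Step 1: age of the ink in each image.** Followed as written, the baseline photograph shows ink applied at the same visit. Visit 3 is at 12 weeks ± 7 days, which is 84 ± 7 = 77 to 91 days. The range holds only if the area is not re-marked.

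**Step 2: does the protocol settle re-marking?** No.
- Sections 7.3.3 and 7.3.4 describe no re-marking.
- Section 7.1.1 lists "Treatment area marking" without a visit limit. Some unrestricted items in that list are done once (demographics) and some at every visit (circumference).
- The schedule of events table has no marking row at any visit, including Visit 1 where marking certainly happens.

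**Step 3: do the marks change visibly by week 12?** This is an inference. Section 2.3.1 gives only an outer limit of one year. The follow-up visits expect the marks still to serve for circumference, "using the marked boundaries as a guide for replication". The marks are therefore meant to remain visible at week 12, but visible does not mean unchanged.

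**Step 4: how strong would a cue have to be?** The documents give no figure for cue strength, so this is an illustration with stated assumptions. Let f be the fraction of pairs revealed by the marks. Assume the device is inert and the remaining pairs are guessed at 50%. The probability of a correct answer is then

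p = f + (1 − f) × 0.5 = 0.5 + f/2,

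and p = 0.80 requires f = 0.6.

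The chance that one reviewer reaches 80% is the binomial tail P(X ≥ r) with n pairs and probability p. The values of n come from section 10.5: 40 estimated, 44 with dropout, up to 50 enrolled.

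| Pairs n | Correct needed r | f = 0.2 | f = 0.4 | f = 0.6 | f for a 50% chance |
|---|---|---|---|---|---|
| 40 | 32 | 0.6% | 11% | 59% | 0.57 |
| 44 | 36 | 0.2% | 6% | 47% | 0.61 |
| 50 | 40 | 0.2% | 8% | 58% | 0.58 |

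**Step 5: averaging over reviewers.** Section 10.4.2 averages over reviewers but does not say how many. Assume three, all of whom see the same revealed pairs, R ~ Binomial(n, f), and guess the rest independently, with total correct guesses ~ Binomial(3(n − R), 0.5). The chance that the average reaches 80% is:

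| Pairs n | f = 0.2 | f = 0.4 | f = 0.6 |
|---|---|---|---|
| 40 | 0.004% | 3% | 55% |
| 50 | 0.0005% | 1.7% | 54% |

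**Step 6: a device with some visible effect.** The inert case needs the strongest cue. If reviewers would score 70% without any cue (an assumption), the expected score is 0.70 + 0.30f, which reaches 0.80 at f = 1/3.

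**The case against.** The strongest objection is that the controlling document is not in the file. Sections 7.3.2 to 7.3.4 send photography to sponsor instructions, and 7.3.2 does the same for marking. Framing, cropping and image preparation may be fixed there. On that view this is a request for documentation and not a design fault. The point stands as a limit: the safeguard is not stated in the supplied text, and blinding is not shown to fail. But the protocol invokes those instructions for taking the photographs and does not mention them in its blinding or primary-analysis sections.

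Second, marks that look the same in both images reveal nothing, and the protocol gives no description of the ink at 12 weeks. That is correct, and the cue is therefore possible, not demonstrated. Re-marking before the week-12 photograph would remove most of the difference in ink age, and the text does not exclude it.

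Third, the probabilities rest wholly on assumed values of f, guessing rate and number of reviewers, and nothing in the file supports f near 0.6. This also stands. The figures show what a cue would need to do, not what it does.

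Fourth, masking could hide skin that reviewers need to see, because the marks follow the treatment boundaries and their size is not given. This is a real cost, and it is why the contour must stay visible.

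None of this removes the gap. The stated sequence of marking, then photographing, then asking which image is earlier allows a cue unrelated to fat, and no stated step closes it.

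**Conclusion.** The concern holds. The photographs used for the primary endpoint show ink marks that the protocol expects to disappear, and no supplied section says these are hidden from reviewers whose task is to put the images in time order. The omission from the supplied text is certain. Whether the marks look different at week 12, and by how much, is not known, so the bias cannot be sized.

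On the illustrative assumptions, marks revealing about one pair in five would almost never carry an inert device past 80%. Marks revealing about three in five would do so roughly half the time. Less is needed if the device has some visible effect. The change should be made because the primary result cannot separate the two sources of correct answers and the remedy is simple. Confidence is medium, because the sponsor's instructions were not available.

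**What to change.** Add to section 10.6.1, with a cross-reference in 10.4.2, wording such as:

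> Before blinded review, the ink marks are digitally masked in the same way in both images of each pair, keeping the abdominal contour visible, and the two images are shown undated and in random order.

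If the sponsor's photograph instructions already require this, cite them there instead. The remedy works whether or not the area is re-marked at follow-up. The analysis population in 10.4.2 stays as it is, and the marks stay on the skin to place the ultrasound and tape measurements.

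The cost is some image preparation, an area of hidden skin whose size the documents do not give, and possibly a lower observed percentage. Subjects have no extra visit or procedure.
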